9.2. BLQ Values / Missing Values

For PK and the PD measure Total Cu parameter calculations, concentrations below the limit of quantification (BLQ) prior to the first measurable concentration will be set to zero; all other BLQ values will be treated as missing. For PUF Cu parameter calculations, all BLQ values will be set to zero.

For PK and PD concentration summaries, BLQ values will be set to zero.

9.3. Pharmacokinetic/Pharmacodynamic Data Presentation Conventions

PK and PD concentration data will be summarized using descriptive statistics (number of participants (N), number of participants with available data (n), arithmetic mean, SD, arithmetic CV, geometric mean (GM), geometric CV, median, minimum and maximum).

The predose PD concentration will be used as baseline; absolute change from baseline will be calculated as: a postdose concentration value – baseline concentration value; percent change from baseline will be calculated as: ([a postdose concentration value – baseline concentration value] / baseline) $\times 100\%$.

The following conventions will be applied to PK/PD presentations and summaries.

- For continuous variables, all mean and median values are formatted to one more decimal place than the measured value. Standard deviation values are formatted to two more decimal places than the measured value. Minimum and maximum values are presented with the same number of decimal places as the measured value.
- Date variables are formatted as DDMMMYYYY for presentation. Time is formatted in military time as HH:MM for presentation.

9.4. Pharmacokinetic Parameters

The following plasma PK parameters will be calculated for total Mo, PUF Mo, and celecoxib using noncompartmental methods with Phoenix® WinNonlin® (Certara USA Inc., Princeton, New Jersey) Version 8.0 or higher or SAS Version 9.4 or higher (SAS Institute Inc., Cary, North Carolina), as applicable. Calculations will be based on the actual sampling times relative to the actual reference ALXN1840 dosing times recorded during the study.

- T_{lag}: time delay between the time of dosing and time of appearance of drug concentration in plasma (for plasma total Mo and PUF Mo with ALXN1840 administration)
- C_{max}: maximum observed concentration in plasma
- T_{max}: time to reach maximum observed concentration in plasma
- AUC_t: AUC from time 0 to the last quantifiable concentration, calculated using the linear trapezoidal rule

- AUC $_{\infty}$: AUC versus time curve from time 0 to infinity, calculated using the linear trapezoidal rule
- % AUC_{extrap}: AUC extrapolated from time t to infinity as a percentage of total AUC $_{\infty}$
- $t_{1/2}$: terminal elimination half-life
- λ_z : apparent terminal-phase elimination rate constant

For ALXN1840, equivalent Mo dose will be used to calculate total Mo (and PUF Mo if applicable) CL/F and Vd/F values: Mo MW of 95.95 Da/ALXN1840 MW of 432.54 Da x 60 mg ALXN1840 = 13.31 mg Mo dose. For celecoxib, use 200 mg dose for the calculation.

- CL/F: apparent oral clearance
- V_d/F : apparent volume of distribution

Additional plasma PK parameters may be calculated if deemed appropriate.

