### 1.2. Schema

Participants will be admitted on Day -1 of each period for Check in procedures. Eligible participants will be randomized on Day 1 immediately prior to dosing in Period 1.

Participants will receive treatment (A or B) based on randomization on Day 1 of each period.

Blood samples for PK analysis of total Mo (as a measure of ALXN1840) and celecoxib will be collected in each period on Day 1 at pre-dose, 1, 2, 3, 4, 5, 6, 8, 12 and 24 hours (Day 2) and then at 24 hour intervals on Days 3, 4, 5, 6, 7, 8, 9, 10, and Day 11. The nominal 336-hour sample for Period 1 will be collected pre-dose in Period 2. Participants will be discharged on Day 11 of each period after completion of all procedures and review of all safety data. The end of study visit (EOS) will occur on Day  $15 \pm 2$  of Period 2, with the collection of 336-hour PK sample for Period 2.

Participants may be asked or required to stay in the CRU between Periods 1 and 2, and/or before the EOS visit, for their own safety, and also to maintain the integrity of the conduct of the study.

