# **3. OBJECTIVES AND ENDPOINTS**

Objectives	Endpoints
Primary	
• To determine the effect of ALXN1840 on the PK of celecoxib, a sensitive CYP2C9 substrate	
 
PK parameters of celecoxib (Cmax, area under the plasma concentration (AUC) versus time curve from time 0 to the last quantifiable concentration [AUCt], and AUC versus time curve from time 0 to infinity [AUC∞]) with and without the coadministration of ALXN1840
 

Secondary	

 
To determine the effect of ALXN1840 on the PK of plasma Mo with the coadministration of celecoxib
 
To determine the safety and tolerability of ALXN1840, with the coadministration of celecoxib
 
	
 
PK parameters for plasma total Mo (Cmax, AUCt, and AUC∞) with the coadministration of celecoxib
 
Safety assessed by incidence of treatment-emergent adverse events (TEAEs) and treatment-emergent serious adverse events (TESAEs), physical examination, vital signs measurements, clinical laboratory and 12-lead electrocardiogram (ECG) results
 

Abbreviations:  $AUC_{\infty}$  = area under the plasma concentration versus time curve from time 0 to infinity;  $AUC_t$  = area under the plasma concentration versus time curve from time 0 to the last quantifiable concentration;  $C_{max}$  = maximum observed plasma concentration of the drug; CYP2C9 = cytochrome P450 2C9; ECG = electrocardiogram; PK = pharmacokinetics; TEAE = treatment-emergent adverse event; TESAE = treatment-emergent serious adverse event.

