#### 8.3.6. Retained and Biobanked Sample

A single biobanked serum sample will be collected pre-dose to serve as a retained safety sample during the study. At the end of the study, pre-dose safety samples will be biobanked to support assay development and determination of normal Cu and Mo levels in healthy participants. Samples may be stored and used for up to 5 years following completion of the study.

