### 9.4.3. Other Analyses

#### 9.4.3.1. Pharmacokinetic and Pharmacodynamic Analyses

Pharmacokinetic analyses will be performed using the PK/PD Analysis Set.

Blood samples for PK analysis of total Mo (as a measure of ALXN1840) and celecoxib will be collected at the following time points: pre-dose and post-dose at 1, 2, 3, 4, 5, 6, 8, 12, 24, 48, 72, 96, 120, 144, 168, 192, 216, 240, and 336 hours in each period.

The following plasma PK parameters will be calculated as endpoints for total Mo and celecoxib using noncompartmental methods with Phoenix® WinNonlin® (Certara USA Inc., Princeton, New Jersey) Version 8.0 or higher or SAS Version 9.3 or higher (SAS Institute Inc., Cary, North Carolina), as applicable. Calculations will be based on the actual sampling times recorded during the study.

- Time delay between the time of dosing and time of appearance of drug concentration in plasma (Tlag; for plasma total Mo with ALXN1840 administration)
- Maximum observed concentration in plasma (Cmax)
- Time to  $C_{max}(T_{max})$
- Area under the plasma concentration (AUC) versus time curve from time 0 to the last quantifiable concentration (AUCt)
- AUC versus time curve from time 0 to infinity (AUC∞)
- AUC extrapolated from time t to infinity as a percentage of  $AUC_{\infty}$  (%AUCextrap)
- Apparent terminal-phase elimination rate constant  $(\lambda_z)$
- Terminal elimination half-life (t/2)
- Apparent oral clearance (CL/F)
- Apparent volume of distribution (Vd/F)

Additional plasma PK parameters may be calculated if deemed appropriate.

Plasma concentrations of total Mo and celecoxib and time deviation data will be presented in a data listing by participant. Plasma concentration data will be summarized separately by analyte and time point for each treatment using the following descriptive statistics: number of participants, arithmetic mean, SD, coefficient of variation (CV), median, minimum, and maximum. Mean plasma concentration versus scheduled time profiles will be presented in figures on both linear and semilogarithmic scales. Individual plasma concentration versus actual time profiles will be presented similarly.

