9.7. Pharmacodynamic Parameters

The following plasma PD parameters will be calculated using noncompartmental methods for Total Cu and PUF Cu (measured and absolute change from baseline) concentrations with Phoenix[®] WinNonlin[®] (Certara USA Inc., Princeton, New Jersey) Version 8.0 or higher or SAS Version 9.4 or higher (SAS Institute Inc., Cary, North Carolina), as applicable. Calculations will be based on the actual sampling times relative to the actual reference ALXN1840 dosing times recorded during the study.

- E_{max}: maximum observed PD concentration in plasma
- TE_{max}: time to reach maximum observed PD concentration in plasma
- AUEC_t: area under the effect versus time curve (AUEC) from time 0 to last quantifiable concentration time, calculated using the linear trapezoidal rule

Additional PD parameters may be calculated as necessary.

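### Total Mo parameters are planned without baseline correction, so if pre-dose Mo is quantifiable the secondary Mo AUC endpoints will overstate exposure from ALXN1840

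*SAP*

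**What the plan says.** Total Mo stands in for the drug. Protocol 9.4.3.1 refers to "Blood samples for PK analysis of total Mo (as a measure of ALXN1840) and celecoxib", and Protocol 3 and SAP 3.3.2 make total Mo Cmax, AUCt and AUC-infinity secondary endpoints.

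For derivation, SAP 9.4 says: "The following plasma PK parameters will be calculated for total Mo, PUF Mo, and celecoxib using noncompartmental methods". Tlag, half-life, CL/F and Vd/F are on the same list. CL/F and Vd/F use the Mo contained in 60 mg ALXN1840, given as 13.31 mg. No baseline adjustment is described.

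Protocol 8.3.6 says that stored pre-dose samples will support "determination of normal Cu and Mo levels in healthy participants".

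For copper, SAP 9.3 sets a baseline rule that covers PD concentrations only: "The predose PD concentration will be used as baseline; absolute change from baseline will be calculated as: a postdose concentration value – baseline concentration value". SAP 9.7 then derives PD parameters for "Total Cu and PUF Cu (measured and absolute change from baseline) concentrations". Mo has no counterpart.

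Under SAP 9.2, a BLQ value before the first measurable one becomes zero. A quantifiable pre-dose Mo value is therefore kept. SAP 11 lists no change on this point.

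**The concern.** Protocol 8.3.6 treats copper and Mo alike, as elements with a normal level in undosed people. The SAP looks at one of them net of baseline and not the other, and gives no reason.

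A background that is small beside Cmax can still matter, because sampling runs to 336 h. AUCt collects the background over the whole window. Late samples, where little drug Mo remains, flatten toward the background, which lengthens the apparent half-life and enlarges the extrapolated area. CL/F then divides a drug-only dose by an area that holds drug plus background. Tlag is meant to show when drug appears, but a Tlag taken from the first measurable concentration loses that meaning if the pre-dose sample is already measurable.

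The bias runs in one direction and does not shrink with more participants. At stake is the description of Mo exposure, not the celecoxib comparison.

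**Working it through.** **The plan's own figure.** 95.95 / 432.54 × 60 = 13.3098, which rounds to the stated 13.31 mg. It reproduces, and it counts drug Mo only.

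**Inputs from the documents**
- Cmax 3.92 µM after a single 60 mg dose (Protocol 2.1).
- Tmax 4.54 h and half-life 51 h for total Mo (Protocol 4.3).
- Twenty sampling times, pre-dose to 336 h (SAP 9.1), and the linear trapezoidal rule (SAP 9.4).

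**Assumptions.** The documents give no endogenous Mo level and no LLOQ. I assume a constant background b, set as a share of Cmax, with every sample quantifiable. The drug profile is one-compartment oral, and λz is fitted to the last five points.

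**Drug-only profile.** ke = ln 2 / 51 = 0.01359 per h. Placing Tmax at 4.54 h gives ka = 0.949 per h. Scaling to 3.92 µM gives:
- AUCt = 306.4 µM·h and AUC-infinity = 309.6 µM·h.
- Concentration at 336 h = 0.044 µM, about 1.1% of Cmax.
- CL/F = (13.31 / 95.95 × 1000) / 309.6 = 138.7 / 309.6 = 0.448 L/h.

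**Adding the background.** AUCt rises by exactly b × 336. AUC-infinity = AUCt + C(336) / λz, where both C(336) and λz now carry the background.

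Worked case at 1% of Cmax (b = 0.0392 µM):
- AUCt rises by 0.0392 × 336 = 13.17, and 13.17 / 306.4 = 4.3%.
- C(336) = 0.0440 + 0.0392 = 0.0832 µM, so background is 47% of that reading.
- Apparent half-life is 68.0 h, so λz = 0.01019 and the extrapolated area is 0.0832 / 0.01019 = 8.16.
- AUC-infinity = 319.56 + 8.16 = 327.7, which is 5.8% above 309.6.

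| Background (% of Cmax) | Cmax | AUCt | AUC-infinity | Half-life | CL/F |
|---|---|---|---|---|---|
| 0.2 | +0.2% | +0.9% | +1.1% | 55 h | −1.1% |
| 1 | +1.0% | +4.3% | +5.8% | 68 h | −5.5% |
| 2 | +2.0% | +8.6% | +12.2% | 83 h | −10.9% |
| 5 | +5.0% | +21.5% | +34.3% | 125 h | −25.5% |

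**Sensitivity to the λz window (3 to 9 points).** Half-life is 61 to 73 h at 1% and 89 to 153 h at 5%. The AUC-infinity excess is about 6% at 1% and 30% to 37% at 5%.

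**Is 51 h already uncorrected?** In the same model I varied the true half-life from 20 to 51 h. A background of 0.5% of Cmax never gave an apparent half-life below about 57 h. A background of 0.2% gives about 51 h when the true value is near 46 h. If 51 h was an uncorrected estimate, the low rows of the table are therefore the more plausible ones.

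**Effect of the fix.** With a constant background, subtracting the pre-dose value returns the drug-only Cmax, AUCt, AUC-infinity, half-life and CL/F exactly.

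**The case against.** The strongest objection is that materiality cannot be shown from the documents. Protocol 8.3.6 concerns stored serum and future assay work. It does not say that Mo is quantifiable in undosed plasma with the PK assay. If pre-dose Mo is BLQ, SAP 9.2 sets it to zero and there is little to correct. Protocol 4.2 expects no measurable ALXN1840 by the EOS Visit, which hints at low late readings without proving them. This stands, and it makes the point conditional. It does not remove it, because the SAP says nothing about what happens if pre-dose Mo is measurable.

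Three further points also stand. The most sensitive parameters (half-life, CL/F, Tlag) are supporting ones, not named endpoints. Mo parameters are only summarised descriptively, and no decision rule uses them. Mo concentrations are listed and summarised by time point, so a pre-dose level would be visible, and SAP 9.4 allows additional parameters. That permits a corrected analysis but does not pre-specify one.

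A reader might also infer that the design is flawed because, with no ALXN1840-alone arm, celecoxib's effect on Mo cannot be estimated. The documents do not support this as a defect. The stated objective is "To determine the effect of ALXN1840 on the PK of plasma Mo with the coadministration of celecoxib", and the endpoint is Mo parameters under coadministration. Celecoxib's effect on Mo is not an objective.

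**Conclusion.** The gap is real: the SAP has no baseline rule for Mo although it has one for copper. If pre-dose Mo is quantifiable, following the plan biases total Mo AUCt and AUC-infinity upward and Cmax slightly. It also lengthens half-life, lowers CL/F and makes a first-measurable Tlag uninformative.

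For an assumed constant background of 0.2% to 5% of Cmax, the excess is about 1% to 21% in AUCt and about 1% to 34% in AUC-infinity. This rests on a one-compartment profile built from the documents' Cmax, Tmax and half-life. The documents do not say how the earlier studies sampled or whether their values were baseline-corrected. If they were not, the low end is more likely, though larger values are not excluded.

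A reader might go further and conclude that the Mo endpoints are certainly contaminated, or that Tlag will be zero in every participant. Either would need a known endogenous level and LLOQ, and the documents give neither.

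The celecoxib mixed model, its geometric mean ratios and the primary conclusion are unaffected. This is a modest pre-specification gap that is cheap to close.

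**What to change.** In SAP 9.4 and 9.5:

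- Report total Mo and PUF Mo parameters for Treatment B twice: as measured, and after subtracting the participant's own Treatment B pre-dose value. That sample precedes the only ALXN1840 dose in both sequences, and Protocol 5.2 excludes prior exposure. If it is BLQ, the two versions coincide.
- Set negative corrected values to zero, and end the corrected AUCt at the last positive corrected concentration.
- Derive Tlag, half-life and CL/F from corrected data.
- Use the Treatment A Mo profile to check that background is stable, in sequence AB only. In sequence BA, Treatment A may follow ALXN1840 by only 14 days. The model leaves about 1.1% of Cmax at 336 h, as large as the smaller backgrounds considered here.

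The cost is SAP wording and one extra parameter table, with no new samples. The downside is slightly more noise, because the correction rests on a single pre-dose value. Keeping the uncorrected results alongside limits that risk.

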# 4. STUDY DESIGN

### 4.1. Overall Design

The study is being conducted as a randomized, 2-period, 2-sequence, cross-over study to determine the effect of a single dose of ALXN1840 (perpetrator) on the single dose celecoxib (victim) kinetics in healthy male and female participants.

The study has a Screening period (Day -28 to Day -2), two 11-day study periods (Day 1 to Day 11) with a minimum of 14 days between doses of celecoxib, and an End of Study (EOS) Visit (Day  $15 \pm 2$  days) after Period 2 dosing. Participants will report to the clinical research unit (CRU) on the day prior (Day -1) to both dosing periods.

All participants will receive 1 treatment in each study period; treatment order will be defined based on randomization:

- Treatment A: One 200 mg celecoxib capsule with 240 mL water (fasting).
- **Treatment B**: One 200 mg celecoxib capsule + 4 × 15 mg ALXN1840 EC tablets with 240 mL water (fasting).

Based on randomization, participants will be administered either Treatment A or Treatment B in each period. A wash-out period of at least 14 days must separate dose administration in Period 1 and Period 2. Participants will remain institutionalized from the day prior to dosing until Day 11 following dose administration for each period.

The PK profile of ALXN1840 and celecoxib will be determined by blood sampling following single dose administration over approximately 5 half-lives or more for both study interventions. Blood sampling for PK assessments will occur at pre-dose, 1, 2, 3, 4, 5, 6, 8, 12, 24, 48, 72, 96, 120, 144, 168, 192, 216, 240, and 336 hours post-dose to ensure full assessment of exposure over time. The nominal 336-hour sample for Period 1 is pre-dose sample for Period 2. In addition to PK sampling, safety and tolerability will be assessed by monitoring AEs, vital signs, 12-lead electrocardiograms (ECGs), and laboratory parameters.

Following scheduled procedures on Day 11, participants will be discharged from the unit. If there are any participants with clinically significant abnormalities at the time of discharge, the Investigator should notify the Medical Monitor prior to discharge, and participants may be asked to remain institutionalized for further clinical monitoring.

Participants may be asked or required to stay in the CRU between Periods 1 and 2, and/or before the EOS visit, for their own safety, and also to maintain the integrity of the conduct of the study.

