### 4.2. Scientific Rationale for Study Design

This study is being conducted in healthy participants so that the assessments are not confounded by disease activity, comorbidities, or concomitant medications. The inclusion and exclusion criteria for this study are consistent with Phase 1 clinical pharmacology studies that assess the medication of interest and to minimize assignment bias.

A 2-way crossover study design was adopted to control the variability within and between participants. Given the desire to evaluate the impact of sequence of administration, the study is being conducted as a 2-sequence, 2-period cross-over study. Blood sampling for PK assessment will include measures for ALXN1840 and celecoxib. Blood sampling timepoints support evaluation of time to reach maximum observed plasma concentration ( $T_{max}$ ) and  $C_{max}$  and include a minimum of 5 half-lives between each study intervention.

The interval between dose administration in each period will be at least 14 days, based on the estimated mean half-life for ALXN1840 of approximately 2 days as previously reported in the bioavailability studies (Studies WTX101-101 and WTX101-102), where healthy participants took an oral dose at 60 mg. Therefore, a minimum of 14 days between dose administration is considered sufficient to eliminate, on average, approximately more than 99.2% of the plasma total Mo before a second dose of celecoxib. The approximately 4-day interval after Period 2 dose administration will also ensure that the participants will have eliminated measurable concentrations of ALXN1840 at the EOS Visit regardless of the randomized dosing sequence. The mean elimination half-life ( $\pm$ SD) of celecoxib after chronic dosing is 11.2 ( $\pm$  3.5) hours (Celebrex®), therefore a minimum of 14-day interval between single dose administrations is sufficient to eliminate greater than 99.2% of plasma celecoxib.

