### Celecoxib

Peak plasma levels of celecoxib occur approximately 3 hours after an oral dose under fasting conditions. Absolute bioavailability studies have not been conducted for this drug. Celecoxib exhibits a dose proportional increase in exposure after oral administration up to 200 mg twice daily and less than proportional increase at higher doses. It has extensive distribution and high protein binding with a half-life of approximately 11 hours (Celebrex®).

Celecoxib metabolism is predominantly mediated via CYP2C9 in the liver. Concomitant administration of fluconazole 200 mg and celecoxib 200 mg resulted in a 2-fold increase in celecoxib plasma concentration. This increase is due to the inhibition of celecoxib metabolism via CYP2C9 by fluconazole. For celecoxib, the selected dose in this study is 200 mg, which has been selected based on the drug interaction study with fluconazole in the Celebrex® US package insert (Celebrex®) and Diflucan® USPI (Diflucan®). A single dose is considered appropriate due to the linear PK of celecoxib within the approved therapeutic dose range.

Celecoxib is formulated into capsules at 50, 100, 200, and 400 mg dose strengths. Celecoxib may be administered initially up to a dose of 400 mg twice daily with adequate safety and tolerability. The dose of 200 mg represents the highest dose within the linear range of the drug to allow DDI assessment (linear PK is thought to be limited by poor absorption above 200 mg). Even though ALXN1840 is considered theoretically and conservatively to have potential for moderate inhibition of CYP2C9 in vitro, because this study is being conducted as a single dose study, without risk of accumulation, no dose adjustment is being made to the dose of celecoxib. A dose of 200 mg is not expected to result in sufficiently high exposure to cause an increase in safety risk.

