9.5. Pharmacokinetic Statistical Analysis

Plasma concentration data for total Mo, PUF Mo, and celecoxib will be summarized separately for each scheduled sampling time using descriptive statistics. Plasma concentrations of total Mo, PUF Mo, and celecoxib and time deviation data will be presented in a data listing by participant. Mean plasma concentration versus scheduled time profiles will be presented in figures on both linear and semilogarithmic scales. Individual plasma concentration versus actual time profiles will be presented similarly.

Pharmacokinetic parameters derived from plasma concentrations of total Mo, PUF Mo, and celecoxib will be presented in data listings and summarized separately using the following descriptive statistics: N, n, arithmetic mean, SD, arithmetic CV, median, minimum, maximum, and 95% confidence interval (CI). Geometric mean and geometric CV will be presented for C_{max} and AUCs only.

The effect of ALXN1840 on celecoxib PK will be assessed using a linear mixed-effect model (SAS PROC MIXED) with treatment condition, sequence, and period as fixed effects and participant nested within sequence as a random effect. The model will be fitted to the natural-log-transformed PK parameters C_{max} , AUC $_{\infty}$ and AUC_t for estimation of effects and construction of CIs for the test treatment (Treatment B: 200 mg celecoxib + 60 mg ALXN1840) compared with the reference treatment (Treatment A: 200 mg celecoxib). The within-participant CV for the corresponding PK parameters will be estimated using the mean squared error from the statistical model. Confidence intervals (90%) will be constructed for the least-squares geometric mean ratio (GMR) estimates between the test and reference treatments for the indicated PK parameters using the natural log-transformed data. The GMR estimates and the associated 90% confidence limits will

be exponentiated back to the original scale. The statistical results will also be graphically presented using a forest plot.

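### The SAP's linear trapezoidal rule overstates celecoxib AUC∞ by about 3.6% to 5.3% at the mean half-life in a one-compartment model; the group B/A ratio shifts by about 1% or less at a true 1.25

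*SAP*

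**What the plan says.** SAP 9.4 covers total Mo, PUF Mo and celecoxib together. AUCt is "AUC from time 0 to the last quantifiable concentration, calculated using the linear trapezoidal rule" and AUC∞ is "AUC versus time curve from time 0 to infinity, calculated using the linear trapezoidal rule". No logarithmic rule for the declining phase is given, and no sensitivity analysis on the rule is planned. Protocol 9.4.3.1 names no rule; it says only that the parameters "will be calculated as endpoints for total Mo and celecoxib using noncompartmental methods".

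The sampling plan in Protocol 4.1 reads "Blood sampling for PK assessments will occur at pre-dose, 1, 2, 3, 4, 5, 6, 8, 12, 24, 48, 72", then every 24 h to 240 h, with a last sample at 336 h. Protocol 4.2 says the mean elimination half-life "of celecoxib after chronic dosing is 11.2" h (SD 3.5 h). Protocol 4.3 adds: "Peak plasma levels of celecoxib occur approximately 3 hours after an oral dose under fasting conditions". Under SAP 9.2, values below quantification before the first measurable one are set to zero, and "all other BLQ values will be treated as missing".

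Celecoxib AUCt and AUC∞ are primary endpoints (SAP 3.3.1). The comparison is specified in SAP 9.5: "Confidence intervals (90%) will be constructed for the least-squares geometric mean ratio (GMR) estimates between the test and reference treatments".

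**The concern.** One 24-h gap is more than two celecoxib half-lives. The linear rule joins the two ends of each gap with a straight line, while an exponential decline lies below that line, so every late gap adds area that is not there. This raises AUC∞ and lowers CL/F.

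The error also depends on half-life. If ALXN1840 slows celecoxib clearance, the half-life under Treatment B lengthens and the error there shrinks, so it need not cancel in B/A. At stake are the reported level of a primary endpoint, the descriptive CL/F and, to a much smaller degree, the ratio itself.

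**Working it through.** The documents state no integration error, so there is no figure of theirs to reproduce.

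**Inputs from the documents.** Half-life 11.2 ± 3.5 h, giving 7.7 to 14.7 h (Protocol 4.2); Tmax about 3 h (Protocol 4.3); nominal sampling times (Protocol 4.1); handling of values below quantification (SAP 9.2); intra-participant CV 0.30 and n = 32 (SAP 4.2); total Mo half-life about 51 h (Protocol 4.3).

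**Assumptions.** One compartment and no lag unless stated; Tmax 2 to 4 h; lower limit of quantification (LLOQ) 0.1% to 5% of Cmax; the half-life after chronic dosing applies to a single dose.

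**Step 1: one gap.** For an exponential decline, linear area / true area = x·coth(x), with x = ln 2 × gap / (2 × half-life).
- 12 h gap, 11.2 h: x = 0.371, factor 1.0455 (+4.6%).
- 24 h gap, 11.2 h: x = 0.743, factor 1.1774 (+17.7%).
- 24 h gap, 51 h (total Mo): x = 0.163, factor 1.0089 (+0.9%).

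**Step 2: share of AUC∞** (half-life 11.2 h, Tmax 3 h). Error added by 12–24 h: 1.21 points; 24–48 h: 3.32; 48–72 h: 0.75; 72–96 h: 0.17. The interval 0–6 h offsets −0.52. Sum: 1.21 + 3.32 + 0.75 + 0.17 − 0.52 = 4.93. The gaps between 6 and 12 h supply the small remainder to the full-profile +5.0% (last sample 96 h). With the last quantifiable sample at 72 h the error is +4.8%, and at 48 h it is +4.1%.

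**Step 3: full profile.** AUC∞ = AUCt + Clast/λz, with λz from the last three quantifiable points, compared with the exact area.

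| One compartment | Linear | Linear-up/log-down |
|---|---|---|
| AUC∞ error, half-life 11.2 h | +3.6% to +5.3% | −0.9% to −0.4% |
| AUC∞ error, half-life 7.7 to 14.7 h | +0.5% to +7.1% | −1.1% to −0.2% |

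At 11.2 h the linear CL/F error follows as 1/1.036 − 1 = −3.5% to 1/1.053 − 1 = about −5%.

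**Step 4: other profile shapes** (terminal half-life 11.2 h).
- Biexponential, no lag, last quantifiable sample at 48 or 72 h: linear error +2.2% to +5.2% in six profiles, four of them above +4%.
- A 0.5-h lag raised the error to between 5% and 7%.
- Biexponential with a marked fast phase, LLOQ 5% of Cmax, last quantifiable sample at 24 h: linear −2.7% to +0.6%; log-down −4.8% to −0.8%, further from the truth than linear in every such case.

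**Step 5: the B/A ratio.** With sustained inhibition, clearance is divided by the true ratio at fixed absorption rate and volume. The group geometric mean ratio is averaged over the half-life spread (1,500 simulated participants per setting).

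| True ratio | Linear | Linear-up/log-down |
|---|---|---|
| 1.10 | 1.096–1.101 | 1.101 |
| 1.25 | 1.240–1.252 | 1.251–1.252 |
| 1.5 | 1.478–1.501 | 1.503 |
| 2.0 | 1.951–1.989 | 2.006 |

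At a true 1.25 the largest shift is 1.240/1.25 − 1 = −0.8%. At a true ratio of 1 both periods carry the same error and it cancels. It also cancels if only bioavailability changes.

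With waning inhibition (true 1.25, half-life 11.2 h), the ratio reads 1.239–1.258 linear and 1.245–1.258 log-down. Linear was closer to the truth in 46 of 60 Tmax and LLOQ settings when inhibition had a 6-h half-life, in 20 of 60 at 12 h and in 14 of 60 at 51 h.

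**Step 6: against the precision.** Half-width on the log scale = t(0.95, 30) × √ln(1.09) × √(2/32) = 1.697 × 0.2936 × 0.25 = 0.1246, that is +13.3%/−11.7%.

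**The case against.** The linear rule is prespecified, is an accepted noncompartmental method, and applies equally to both treatments in each participant. The objective is a ratio, not celecoxib's absolute exposure. SAP 4.2 plans at a true ratio of 1, where the error cancels, and SAP 4.1 says that a result outside 80% to 125% is not a failed study. All of this stands, and it is why the point is minor.

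It also stands that the size of the error rests on an unstated assay limit and an assumed profile shape, and that log-down is not uniformly better (Steps 4 and 5). What does not stand is the claim that a crossover removes the error. It remains in AUC∞ and CL/F levels, and it cancels in the ratio only when the half-life is unchanged.

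A reader might go further and infer that the primary ratio is materially biased towards no interaction. The documents do not support that. The group shift at 1.25 is under 1%. The larger rows lie far out: Protocol 2.1 reports a simulated ratio of 1.5 at 240 mg, four times the study dose. Nor is the direction fixed. A single participant's true 1.25 can read 1.280–1.288 when the last quantifiable sample is at 24 h under A and 48 h under B, but inflation occurred in only 8% of the settings examined and largely averages out in the group ratio.

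**Conclusion.** The point holds as a minor accuracy issue. In a one-compartment model with no lag, Tmax 2 to 4 h and LLOQ 0.1% to 5% of Cmax, the linear rule overstates celecoxib AUC∞ at the mean half-life by 3.6% to 5.3%. The overstatement persists under biexponential disposition when quantification reaches 48 h or later, but it can vanish or turn negative when the last quantifiable sample is at 24 h.

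For the group ratio, the effect at a true 1.25 under sustained inhibition is about 1% or less, roughly a tenth of the CI half-width. It does not threaten the study's conclusion. If inhibition wanes quickly, changing the rule brings no dependable gain in the ratio. I make no claim about the direction of any effect on the AUCt ratio.

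**What to change.** In SAP 9.4, for celecoxib only, calculate AUCt and AUC∞ by the linear-up/log-down trapezoidal rule, and report the linear rule as a sensitivity analysis. No change is proposed for total Mo, where the error is about 0.9% per 24-h gap, or for PUF Mo. SAP Section 11 needs no entry, because the protocol specifies no integration rule.

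The cost is one software setting and one SAP phrase. There are three downsides:
- A residual AUC∞ error remains: about −1.1% to −0.2% in one compartment, and up to about −5%, worse than linear, with a marked distribution phase and a last quantifiable sample at 24 h.
- Under short-lived inhibition the ratio can be marginally further from the truth.
- Results may not be computed identically to earlier studies, whose rule the documents do not state.

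Reporting the linear rule alongside makes all three visible.
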